### Subgroup Analysis Set

Subgroup analyses will be performed on primary and key secondary efficacy endpoints based on the subgroups as defined below.

In order to include baseline variables in the Cox proportional hazards model for OS and PFS multivariate analysis, and the logistic model for BOR multivariate analysis, indicator variables will be defined for each subgroup category except for the reference category, against which all other categories are compared. In case a low number of subjects (i.e. < 5% of the randomized population) is observed in a given subgroup category, categories may be pooled. Subgroup analyses will not be performed on or include any subjects with missing values for a given subgroup.

In addition, primary and key secondary endpoint tables will be repeated for the group of subjects who are treated in Japan. Japan-specific outputs will follow the format of the overall primary/secondary end-point tables and will display one-sided p-values. These tables will omit the geographically-stratified analysis.

The parameterization used for the primary analysis will be updated and finalized at the Data Review Meeting, at the latest, and documented in an amendment to this SAP, should it differ from the following definitions.

The subgroups are as follows:

- PD-L1 Assay Status – Tumor cells
    - < 1% (Reference)
    - $\geq 1\%$
  - Age Group 1
    - Age at randomization < 65 years (Reference)
    - Age at randomization  $\geq 65$  years
  - Age Group 2
    - Age at randomization < 75 years (Reference)
    - Age at randomization  $\geq 75$  years
  - Gender
    - Male (Reference)
    - Female
  - Race
    - Caucasian / White (Reference)
    - Asian
-

- Black/ African American
  - Other
  - Pooled Geographical Region:
    - Asia
    - Non-Asia (Reference)
  - ECOG PS at Maintenance Phase baseline
    - ECOG PS 0
    - ECOG PS 1 (Reference)
  - Site of primary tumor
    - Stomach
    - Gastro-esophageal Junction (GEJ) (Reference)
  - Regimen of induction chemotherapy
    - Oxaliplatin + 5-FU (Reference)
    - Oxaliplatin + Capecitabine
  - Re-Baseline Response per Independent Radiologist
    - CR, PR (Reference)
    - SD, non-CR/non-PD
  - Microsatellite Instability Biomarker Status
    - Stable (Reference)
    - High
  - Presence of Liver Metastasis
    - Diagnosis of metastatic liver
    - No diagnosis of metastatic liver (reference)
  - Presence of Peritoneal Carcinomatosis
    - Diagnosis of peritoneal carcinomatosis
    - No diagnosis of peritoneal carcinomatosis (reference)
  - Prior Gastrectomy
    - Prior gastrectomy
    - No prior gastrectomy (reference)
-

- Number of Metastatic Sites
  - 0 (reference)
  - 1
  - 2
  - $\geq 3$

## 10 General Specifications for Statistical Analyses

For the Induction Phase, all the analyses performed will be presented by the two chemotherapy arms and overall, unless otherwise specified. For the Maintenance Phase, demographic and baseline characteristics, as well as all the safety and efficacy endpoint analyses will be summarized by avelumab arm and the combined chemotherapy/BSC arm.

All statistical analyses will be performed using SAS® Version 9.4 or higher.

### Data handling after cut-off date:

Data after the cut-off date may not undergo the cleaning process and will not be displayed in any listings or used for summary statistics, statistical analyses or imputations.

### Pooling of centers:

In order to provide overall estimates of treatment effects, data will be pooled across trial centers. The “center” factor will not be considered in statistical models or for subgroup analyses due to the high number of participating centers and the small number of subjects expected to be randomized at each center.

### Significance level:

The overall significance level is 2.5%, one-sided. The confirmatory statistical tests for the primary and key secondary efficacy endpoint analyses are described in Sections 15.1 and 15.2. Section 7 describes the procedures for controlling the overall type I error rate in the study. The statistical tests to compare treatment arms on other secondary, CCI [REDACTED], and safety analyses CCI [REDACTED] [REDACTED]

Confidence intervals will be two-sided with a confidence probability of 95%, unless otherwise specified.

### Presentation of continuous and qualitative variables:

Continuous variables will be summarized using descriptive statistics i.e., number of non-missing values and number of missing values, [i.e., n (missing)], mean, median, standard deviation (StDev),

---

minimum, maximum and first and third quartile (Q1 and Q3). As per general reporting conventions, mean, median, Q1, and Q2 will be displayed with one more decimal place than the raw data; StDev will be displayed using two more decimal places than the raw data. Percentages will be reported to one decimal place. Rounding will be performed to closest integer/decimal using the common mid-point between the two consecutive values – e.g. 5.1 to 5.4 will be rounded to an integer of 5, and 5.5 to 5.9 will be rounded to an integer of 6.

Qualitative variables will be summarized by frequency counts and percentages. Unless otherwise stated, the calculation of proportions/percentages for a given qualitative variable will include subjects with missing values in the denominator. When applicable, counts of missing observations for a qualitative variable will be presented on summary tables.

In case the analysis refers only to certain visits, percentages will be based on the number of subjects who had some study procedure performed at that visit, unless otherwise specified.

**Study Treatment Phases:**

The Induction Phase refers to the open-label chemotherapy treatment phase during which subjects receive chemotherapy comprised of oxaliplatin and either 5-fluorouracil (5-FU) or capecitabine. The induction treatment phase is defined as the period from the date of the first administration of induction chemotherapy through the date of the Induction Phase End-of-Treatment visit or the day before randomization.

The Maintenance Phase refers to the study treatment period in which randomized subjects receive their study treatment: either avelumab or the treatment prespecified by the physician (either continuation of the Induction Phase chemotherapy regimen, or BSC). The maintenance treatment phase is defined as the time from randomization to the Maintenance Phase End-of-Treatment visit.

**Table 2 Definition of Reference Date by Treatment Phase**

Treatment Phase	Reference Start Date	Reference End Date
Induction Phase	First dose of induction chemotherapy treatment	Date of end of study or death date, whichever comes later, for subjects who were not randomized; Randomization Date – 1 day for subject who were randomized.
Maintenance Phase	Randomization	Date of end of study or death date, whichever comes later

Listings will include all subject data as collected in the clinical database but data corresponding to different treatment phases will be presented separately.

**Re-Baseline Tumor Scan:**

Per the study protocol, following completion of Induction Phase chemotherapy treatment, re-evaluation of inclusion/exclusion criteria, safety parameters, and HRQoL assessments is to be

performed at the Re-Baseline visit, which should occur within the 10-day Re-baseline period. Additionally, a Re-Baseline tumor scan must be performed in order to assess eligibility for randomization into the Maintenance Phase (see Section 5) and to establish the “baseline” state to which Maintenance Phase tumor scans shall be compared, when assessing overall response.

The Re-Baseline tumor scan is the scan evaluated by the independent radiologist to determine the subject’s eligibility for randomization into the Maintenance Phase. This scan is clearly identified in the data transfer from the independent radiologist. The investigator assessment of this scan will be the baseline for RECIST v1.1 assessments during the Maintenance Phase.

**Tumor Response for Efficacy Analyses:**

For all endpoint analyses that employ use of tumor response, the tumor response will be determined according to RECIST 1.1, as per investigator assessment, and is measured relative to the Re-Baseline scan.

**Definition of baseline:**

For the Induction Phase, baseline is defined as the last measurement taken prior to the first dose of open-label chemotherapy treatment during the Induction Phase.

For the Maintenance Phase, baseline is defined differently based on analysis type and randomized treatment. For subjects randomized to receive active study medication (avelumab or continuation of Induction chemotherapy), baseline for safety analyses is defined as the last measurement taken prior to the first dose of randomized treatment. For subjects randomized to receive BSC-only, baseline for safety analyses is defined as the last measurement taken on or before the Maintenance Phase Week 1 Day 1 visit. For all subjects, baseline for efficacy analyses is defined as the last measurement prior to randomization. Baseline for heart rate and QTc assessments will be derived from the visit where both heart rate and QT are not missing.

If an assessment is planned to be performed on Week 1, Day 1 per the protocol and the assessment is performed on the same day as the first dose of study treatment, it will be assumed that it was performed prior to study treatment administration if assessment time point is not collected or is missing. If assessment time points are collected, the observed time point will be used to determine pre-dose on study day 1 for baseline calculation. Unscheduled assessments will be used in the determination of baseline. However, if time is missing, an unscheduled assessment on study day 1 will be considered to have been obtained after study treatment administration.

If both central and local labs are collected in a study, the baseline will be derived based only on the central lab collected data.

Subjects who start treatment and discontinue from the study on the same day may have two different sets of data collected on study day 1 (one during study and one in the End of Treatment (EOT) visit. Data reported at the EOT visit are not eligible for baseline selection.

If a scheduled pre-dose measurement actually occurred post-dose, then the corresponding measurement will be treated and analyzed similar to an unscheduled post-dose measurement.

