Concomitant procedures	Collected from Screening through End-of-Treatment Visit						
AE and SAE collection	Collected from Informed Consent through End-of-Treatment Visit ^b						X
Samples and Laboratory Assessments							
Hematology and hemostaseology ^g	X	X	X	X	X	X	X
Full serum chemistry ^h	X					X	
Core serum chemistry ^h		X	X	X	X		X
Urinalysis ⁱ	X					X	X
β-hCG pregnancy test ^j	X	X	X	X	X	X	
HBV and HCV test ^k	X						
T ₄ and TSH	X			X		X	

Dosing						
Premedication [¶]		X	X	X	X	
Chemotherapy administration		X	X	X	X	

AE = adverse event; β -hCG = β -human chorionic gonadotropin; CT = computed tomography; D = day; ECG = electrocardiogram; ECOG PS = Eastern Cooperative Oncology Group Performance Status; EOT = end of treatment; HBV = hepatitis B virus; HCV = hepatitis C virus; ICF = informed consent form; CCI [redacted]; CCI [redacted]; RNA = ribonucleic acid; SAE = serious adverse event; T₄ = free thyroxine; TSH = thyroid-stimulating hormone; W = week.

- a A time window of up to 4 days before or 2 days after the scheduled Day 1 visit (-4 / +2 days) will be permitted for all trial procedures for the Day 1 visit of each cycle. Subjects should also return to the trial site as per local institutional practice for any additional routine assessments during chemotherapy.
- b Subjects who discontinue the Induction Phase due to any reason will have an EOT visit within 7 days of the decision to discontinue chemotherapy. All subjects who do not enter the Maintenance Phase will have a 30-day after last treatment Safety Follow-up visit. Subjects entering the Maintenance Phase will have the Re-baseline visit (Table 3 to Table 6 as applicable). Subjects with an AE ongoing at the EOT visit must be followed up for final outcome until the 30-day Safety Follow-up visit. Subjects with an SAE ongoing at the 30-day Safety Follow-up visit must be monitored and followed up by the Investigator until stabilization or until the outcome is known, unless the subject is documented as “lost to follow-up.”
- c Subjects who complete Cycle 4 will return to clinic for the Re-baseline visit (see Table 3 to Table 6 depending on regimen). The Re-baseline visit is to occur -10 to -1 days before the first administration in the Maintenance Phase.

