Additionally, subjects receiving avelumab who have experienced a CR should be treated for a minimum of 12 months or until disease progression or unacceptable toxicity, after confirmation of response. In case a subject with a confirmed CR relapses after stopping treatment, but prior to the end of the trial, 1 re-initiation of treatment is allowed at the discretion of the Investigator and after agreement with the Medical Monitor. In order to be eligible for retreatment, the subject must not have experienced any toxicity that led to treatment discontinuation of the initial avelumab therapy. Subjects who re-initiate treatment will stay on trial and will be treated and monitored according to the protocol and follow the Schedule of Assessments until disease progression (see [Table 3](#)).

The treatment should start within 4 days after randomization. While on trial treatment, subjects will be asked to visit the trial site as specified in the Schedule of Assessments (see [Table 3](#), [Table 4](#), [Table 5](#), and [Table 6](#)).

For both avelumab and maintenance chemotherapy, a time window of up to 4 days before or 2 day after the scheduled visit day (-4/ +2 days) will be permitted for all trial procedures. Subjects should return to the target date even if the previous visit was off schedule.

The tumor evaluation (see [Section 7.3](#)) will be performed every 6 weeks (for the first 12 months and every 12 weeks thereafter) with a time window of -5 days for both avelumab and maintenance chemotherapy.

Subjects will receive either:

- Avelumab by IV infusion following pretreatment (see [Section 5.1.2.2.1](#)) once every 2 weeks (see [Section 6.2.1](#)), or
- Maintenance chemotherapy following pretreatment as applicable prior to each infusion (see [Section 6.2.2](#)).

Assessments to be performed during the Maintenance Phase are presented in [Table 3](#) to [Table 6](#).

During the treatment period, the following assessments and procedures will be performed (see [Table 3](#) to [Table 6](#) for the detailed schedule):

- The subject-reported outcomes/QoL assessments will be completed by subjects prior to any trial-related procedures (time points outlined in [Table 3](#) to [Table 6](#)) and then every 6 weeks thereafter.
- AEs and concomitant medications and procedures will be documented at each visit.
- ECOG PS will be assessed at each treatment visit.

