**Definition of Maintenance Phase baseline in the context of HRQoL assessments:**

Maintenance Phase baseline for HRQoL assessments is defined as the last available assessment conducted prior to or on the date of randomization, occurring no more than 28 days prior to randomization. If no such assessment exists, Maintenance Phase baseline will be the last available assessment after randomization and prior to the first dose of Maintenance Phase treatment.

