**Definition of Induction Phase Study Day:**

Induction Phase Study Day is defined relative to the date of first administration of induction chemotherapy. Induction Phase Study Day 1 corresponds to the day of first administration of induction chemotherapy and the day before is defined as Induction Phase Study Day -1 (i.e., no Induction Phase Study Day 0 is defined).

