**Definition of Maintenance Phase Study Day:**

Maintenance Phase study day is defined relative to the date randomization into Maintenance Phase. Maintenance Phase study day 1 corresponds to the day of randomization and the day before is defined as Maintenance Phase Study day -1 (i.e., no Maintenance Phase study day 0 is defined).

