**Definition of treatment day:**

Treatment day is defined relative to the start date of study treatment within a given Treatment Phase. Treatment Day 1 is defined as the first day study treatment within a given Phase; Treatment Day -1 is defined as the day prior to the start of the given treatment. Treatment Day 0 is not defined. For example, for the Induction Phase, Treatment Day 1 is defined as the first day of Induction Phase chemotherapy and the day before is defined as Treatment Day -1. Similarly, for subjects randomized to active treatment during Maintenance Phase, Treatment Day 1 is defined as the day the first dose of Maintenance Phase study drug was given. For subjects randomized to receive BSC-only during Maintenance Phase, Treatment Day 1 is defined as the date of the Week 1 Day 1 assessment visit.

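### In the Maintenance Phase, the SAP's rule for untimed unscheduled values is keyed to study day 1 (the randomization day), although the safety baseline is anchored to the first dose

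*SAP*

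**What the plan says.** SAP Section 10, under the definition of baseline, sets the Maintenance safety baseline for subjects on active treatment by reference to dosing: "baseline for safety analyses is defined as the last measurement taken prior to the first dose of randomized treatment". Unscheduled assessments may serve as baseline. For same-day values the section distinguishes two cases:

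- A test planned for Week 1 Day 1 and done on the day of first dose is presumed pre-dose if its time is missing.
- An unscheduled test is handled by a different rule: "However, if time is missing, an unscheduled assessment on study day 1 will be considered to have been obtained after study treatment administration".

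The same section of the SAP then defines its day terms separately:

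- For Induction: "Induction Phase Study Day 1 corresponds to the day of first administration of induction chemotherapy".
- For Maintenance: "Maintenance Phase study day 1 corresponds to the day of randomization".
- For the Maintenance dosing day of actively treated subjects: "Treatment Day 1 is defined as the day the first dose of Maintenance Phase study drug was given".

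Protocol Section 7.1.4 sets the interval between the two Maintenance dates: "The treatment should start within 4 days after randomization".

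**The concern.** The rule for untimed unscheduled values exists to stop a value that may have been taken after the infusion from serving as a pre-treatment baseline. To do that it must act on the day of first dose. In Induction it does, because study day 1 and the first-dose day coincide. In Maintenance the SAP gives the two days different names, and the rule uses the name for the randomization day.

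The outputs at stake are the safety tables that depend on baseline: maximum change in vital signs (SAP 16.4), the change-based ECG criteria (SAP 16.5.1) and the laboratory shift and change-from-baseline tables (SAP 16.3.1). A baseline picked from the wrong side of the first dose distorts the change shown for that subject. A programmer who follows the SAP's own definitions would implement something other than what the section appears to intend.

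**Working it through.** The plan gives no figure to reproduce. The check traces the definitions and uses one line of arithmetic.

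**Inputs**
- Maintenance study day 1 is the randomization day, with no day 0 (SAP 10, Maintenance Phase Study Day).
- The first-dose day is Treatment Day 1 (SAP 10, treatment day).
- The gap from randomization to first dose is 0 to 4 days (Protocol 7.1.4).

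**Step 1. Can the two dates differ?** Yes, and the documents expect it. Protocol Table 1, footnote c, says: "The Re-baseline visit is to occur -10 to -1 days before the first administration in the Maintenance Phase". Tables 3 to 6 mark randomization in the Re-baseline column, ahead of the Day 1 dosing column. The SAP's fallback for the HRQoL baseline allows for "the last available assessment after randomization and prior to the first dose of Maintenance Phase treatment", which presupposes an interval. The SAP equates the two dates only as an imputation, when the Maintenance start date is missing or incomplete (SAP 10, Exposure).

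**Step 2. On which study day does the first dose fall?** Study day of first dose = gap in days + 1.

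| Gap (days) | Study day of first dose | Does the rule act on the dosing day? |
|---|---|---|
| 0 | 0 + 1 = 1 | Yes |
| 1 | 1 + 1 = 2 | No |
| 2 | 2 + 1 = 3 | No |
| 3 | 3 + 1 = 4 | No |
| 4 | 4 + 1 = 5 | No |

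**Step 3. An untimed unscheduled value on the randomization day (gap of 1 day or more).** No Maintenance drug has been given, yet the rule declares the value post-treatment, so it cannot be baseline. It also precedes the on-treatment period, which starts at first dose, and the safety tables summarize on-treatment records only. It therefore enters neither side of the comparison. Protocol Table 6 plans vital signs, weight, hematology and core chemistry at Week 1 Day 1. For those tests the planned value is later, is presumed pre-dose if untimed, and would normally be the baseline anyway. The loss matters for tests not planned at that visit: ECG, T4/TSH and the analytes found only in full chemistry.

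**Step 4. An untimed unscheduled value on the first-dose day (gap of 1 day or more).** The unscheduled rule does not reach it, because the day is not study day 1. The pre-dose presumption does not reach it either, because that covers only tests planned for Week 1 Day 1. The general definition requires a value before first dose, but without a time nothing settles whether this one qualifies. Unscheduled values are eligible in principle, so it could be selected.

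**Step 5. Reach.** The efficacy baseline is anchored to randomization, and HRQoL and ECOG PS have their own baseline rules. BSC-only subjects use values on or before the Week 1 Day 1 visit. The laboratory baseline uses central results only. What remains is the Maintenance safety baseline of actively treated subjects for vital signs, ECG and central laboratory tests.

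**The case against.** The strongest reply is that the intended meaning is clear. The section writes study day 1 without naming a phase. Its companion rule for planned tests refers expressly to the day of first dose, and its remark about subjects who start and stop treatment on one day makes sense only for the dosing day. On that view this is a loose term and not a chosen method. That stands as an account of intent. It does not remove the problem, because the only Maintenance definition of the term is the randomization day and the SAP already has another name for the day that was meant.

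A reader might infer more: that a post-infusion value will become the baseline, hide an infusion reaction, and do so mainly in the avelumab arm. Suppose, with assumed values, a pre-dose temperature of 36.8 °C and an untimed unscheduled 39.0 °C at first infusion. The increase is 39.0 − 36.8 = 2.2 °C, in the 2 to <3 °C category of SAP Table 9. With 39.0 °C as baseline and no later higher value, it falls in the <1 °C category. The documents do not support presenting this as the expected result:

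- On the dosing day the status of the value is undefined; the SAP does not assign it to baseline. The presumption for planned tests does not cover it.
- Local laboratory results, which the protocol allows for safety management, cannot become baseline.
- Worst-grade laboratory tables, liver-test thresholds, and the absolute QTc and QRS criteria do not depend on baseline.
- Infusion reactions are also captured as adverse events under SAP Appendix IV, including pyrexia and hypotension on the infusion day.
- The protocol lists infusion-related reactions as a known avelumab risk, but Sections 5.1.2.2.2 and 6.5.4 also anticipate hypersensitivity or infusion reactions with chemotherapy. A differential effect by arm is conjecture.

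It would also be too strong to call randomization-day values lost. All vital signs and ECGs are listed, with those outside the on-treatment period flagged.

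**Conclusion.** The rule is wrong as written under the SAP's own definitions. It acts on the dosing day only when dosing falls on the randomization day. For gaps of 1 to 4 days it excludes a value that is certainly pre-dose and leaves the status of a first-dose-day value open.

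The practical size is minor. A subject is affected only if actively treated, dosed on a later day than randomized, and with an untimed unscheduled assessment on one of those two days. For the randomization day it must usually also be a test not planned at Week 1 Day 1. The documents give no count of such values and do not show how often assessment times are missing; the number is probably small. OS, PFS, BOR, alpha and power are not affected. The conclusion assumes that a programmer applies the section's defined terms literally. If the dosing day is substituted informally, the tables come out as intended but the written plan does not describe them.

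**What to change.** In SAP Section 10, under the definition of baseline:

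1. Replace study day 1 with Treatment Day 1 in all three places.
2. State that, for subjects receiving active treatment, an untimed unscheduled value on Treatment Day 1 is post-dose, and that values on earlier days, including the randomization day, are pre-dose.
3. Keep the existing rule for BSC-only subjects, whose baseline takes values on or before the Week 1 Day 1 visit. For them Treatment Day 1 is that visit and no dose is given, so applying item 2 to them would create a new conflict.

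With this wording the rule falls on the dosing day for every gap from 0 to 4 days. The cost is a short SAP wording change and one date variable in the baseline derivation.
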